### 9.3.3.4 Definition of COPD severity

Severity of COPD will be evaluated among new users of olodaterol and indacaterol that have a recorded diagnosis of COPD before the index date. Severity of COPD will be evaluated at the index date by a modified version of the algorithm developed by Verhamme and colleagues [[P11-13226](#)] (see [Table 7](#)).

Table 7 Definition criteria of COPD severity

| Severity of COPD | Definition   |
|-------------------------|---|
| Mild                    | Less than 2 dispensings of the same COPD drug class with a maximum interval of 6 months in the 12 months before the index date.   |
| Moderate                | Regular bronchodilator treatment, defined as having at least 2 dispensings of the same COPD drug class with a maximum interval of 6 months in the 12 months before the index date   |
| Severe                  | Occurrence of at least one of the following events in the year before the index date: 
 
• Hospitalisation for COPD
 
• Recorded diagnosis of pneumonia
 
• Third course of antibiotics for respiratory tract infections
 
• Second course of systemic corticosteroids for the treatment of COPD exacerbation
 
 |
| Very severe             | Occurrence of at least one of the following events in the year before the index date unless other time period is specified: 
 
• Dispensed oxygen therapy
 
• Dispensed nebuliser therapy
 
• Diagnosis of emphysema at any time before the index date
 
   |

COPD = Chronic Obstructive Pulmonary Disease.

Sources: modified from Verhamme et al., 2012 [[P11-13226](#)]; Soriano et al., 2001 [[R08-1492](#)]; and Curkendall et al., 2006. [[P07-09136](#)]

1 Severity criteria also included in definition from Soriano et al., 2001. [[R08-1492](#)]

2 Severity criteria also included in definition from Curkendall et al., 2006. [[P07-09136](#)]

The use of antibiotics and oral corticosteroids and hospitalisations for COPD haven been used by other authors as markers of severity of COPD exacerbations. [[P12-09396](#)] [[P12-09395](#)] [[P12-14293](#)]

The operational definitions to be applied when assessing the severity of COPD are as follows:

- Same-class bronchodilators. The following bronchodilators classes will be considered (see [Annex Table 4:2](#)):

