  - Inhaled short-acting muscarinic antagonists (SAMAs)
  - Inhaled long-acting muscarinic antagonists (LAMAs)

- Inhaled short-acting beta2-agonists (SABAs)
- Inhaled LABAs
- Inhaled glucocorticosteroids (ICSs)
- Fixed combinations of SABAs and SAMAs
- Fixed combinations of SABAs and ICSs
- Fixed combinations of LABAs and ICSs
- Systemic glucocorticosteroids
- Systemic beta2-agonists
- Xanthines
- Roflumilast
- Hospitalisation for COPD
  - Primary or secondary hospital discharge diagnosis for COPD
  - ICD-10 codes: J40-J44; ICD-9 codes: 491, 492, 496
- Recorded diagnosis of pneumonia
  - Primary or secondary hospital discharge diagnosis for pneumonia
  - ICD-10 codes J09-J18; ICD-9 codes: 480-486
- Third course of antibiotics for respiratory tract infections
  - A course with antibiotic is defined as that involving consecutive dispensings of antibiotics with less than 7 days between the end of days of supply of one dispensing and the date of the next dispensing
  - ATC codes for antibiotics: J01 (antibacterials for systemic use)
- Second course of systemic glucocorticosteroids for the treatment of COPD exacerbation
  - A course with systemic corticosteroids is defined as that involving consecutive dispensings with less than 7 days between the end of days of supply of one dispensing and the date of the next dispensing.
  - ATC codes for systemic glucocorticosteroids: H02AB
- Oxygen therapy, ATC code: V03AN01
- Nebuliser therapy (to be identified in each database using national drug codes)
- Primary or secondary hospital outpatient or inpatient discharge diagnosis of emphysema at any time before the index date
  - ICD-10 code: J43; ICD-9 code: 492

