### ANNEX 3. EVALUATION OF COPD SEVERITY IN AUTOMATED HEALTH DATABASES

Annex Table 3:1 Published definitions of COPD severity in studies conducted in automated health databases

| Reference, Severity Criteria  | COPD Severity  |  |   |
|---|--|--|---|
|   | Mild   | Moderate   | Severe  |
| Integrated Primary Care Information Project, Netherlands [P11-13226]   |  |  |   |
| 
With spirometry data, used GOLD criteria [P13-02399]
 
Without spirometry, used methods of Curkendall et al., [R09-0579] Eisner et al., [R13-1392] and Soriano et al. [R08-1492]
  | At initial COPD symptoms   | At least 2 prescriptions of bronchodilators of the same drug class with a maximum interval of 6 months in 1 year | 
Severe:
 
 
• Hospitalisation for COPD, or
 
• Third course of antibiotics for respiratory infection in 1 year, or
 
• Second course of systemic corticosteroids for COPD exacerbation in 1 year
 
 
Very severe:
 
 
• Oxygen therapy, or
 
• Scheduled for lung transplant
 
 |
| Saskatchewan Health, Canada [R09-0579]   |  |  |   |
| 
Case-control study to find severity marker variables, using:
 
 
• Pre-existing chronic conditions
 
• Recent acute conditions
 
• Recent high use of bronchodilators
 
 
Specific components of the above are detailed in the article's appendix
 | Patients ranked into 5 quintiles by likelihood of COPD hospitalisation, from conditional logistic regression model |  | 
Factors in previous 180 days associated with severe COPD:
 
 
• Emphysema
 
• Recent nebuliser use
 
• Home oxygen therapy
 
• Corticosteroid use
 
• Frequent bronchodilator use
 
• Pneumonia
 
• Previous COPD exacerbation
 
   |

Proprietary confidential information © 2014 Boehringer Ingelheim International GmbH or one or more of its affiliated companies

Annex Table 3:1 (con't) Published definitions of COPD severity in studies conducted in automated health databases

| Reference, Severity criteria   | COPD Severity              |   |   |
|--|----------------------------|---|---|
|  | Mild                       | Moderate  | Severe  |
| General Practice Research Database, United Kingdom Soriano [R08-1492] |                            |   |   |

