5.3.3 Severity of COPD

Severity of COPD will be evaluated among new users of olodaterol and indacaterol that are aged 40 years or older and have a recorded diagnosis of COPD (with or without a diagnosis of asthma) ever before or up 30 days after the index date. The population aged 40 years or older is considered the most likely to have COPD and is frequently selected in studies to evaluate medication use among patients with COPD [[P07-07347](#), [P11-13226](#), [P07-09136](#)]. Patients aged 39 years or younger with a diagnosis of COPD will still be considered as

Proprietary confidential information © 2017 Boehringer Ingelheim International GmbH or one or more of its affiliated companies

having COPD and described separately if there are at least 5 patients in each COPD severity category. Definitions shown in [Table 8](#) will be adapted to the characteristics and data availability in each data source; database-specific specifications have been described in [Section 9.2](#). The four severity categories will be mutually exclusive, and patients that fulfil criteria for more than one category will be classified as being in the more severe category.

Table 8 Definition criteria of COPD severity (adapted primarily from Verhamme et al., 2012 [[P11-13226](#)])

Severity of COPD	Definition
Mild	Less than two prescriptions/dispensings of drugs for obstructive airways disease of the same class in any 6-month interval in the 12 months before the index date (i.e., 0 or 1 prescriptions/dispensings of the same COPD drug class in the 12 months before the index date, or if ≥ 2 prescriptions/dispensings, these have to be more than 6 months apart)
Moderate	Regular bronchodilator treatment, defined as having at least two prescriptions/dispensings of the same COPD drug class with an interval of ≤ 6 months in the 12 months before the index date ^{1,2}
Severe	Occurrence of at least one of the following events in the 12 months before the index date: 
 • Hospitalisation for COPD exacerbation¹ • At least two COPD exacerbations without hospitalisation, where COPD exacerbation is defined by any of the following³: 
 • A course of antibiotics for lower respiratory tract infection (acute bronchitis or pneumonia)¹ • A course of systemic corticosteroids for the treatment of COPD exacerbation¹ • A diagnoses of COPD exacerbation without hospitalisation

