Very severe	Occurrence of at least one of the following events in the 12 months before the index date unless another time period is specified: 
 • Dispensed oxygen therapy^{1,2} • Dispensed nebuliser therapy^{1,2} • Diagnosis of emphysema at any time before the index date¹

COPD = Chronic Obstructive Pulmonary Disease.

- 1 Severity criteria also included in definition from Curkendall et al., 2006 [[P07-09136](#)].
- 2 Severity criteria also included in definition from Soriano et al., 2001 [[R08-1492](#)].
- 3 Severity criteria modified to align with the Global Initiative for Chronic Obstructive Lung Disease (GOLD) 2016 definition for severity categories C and D [[P16-00121](#)]. If two or more of these criteria occur within a 21-day time period, they will be considered part of the same exacerbation episode and counted only once. If one or more of these criteria occur within a 21-day period of a hospitalisation for COPD, this will be considered part of the same “COPD exacerbation with hospitalisation” episode.

Sources: modified from Verhamme et al., 2012 [[P11-13226](#)]; Soriano et al., 2001 [[R08-1492](#)]; Curkendall et al., 2006 [[P07-09136](#)]; and GOLD, 2016 [[P16-00121](#)].

Because data on hospitalisations are not available in the IMS RWE LPD database, COPD severity will not be described in this database.

The proposed operational definitions to be applied when assessing the severity of COPD are as follows:

- Same-class “drugs for obstructive airways disease”: medications listed in [Annex Table 1-6](#) will be identified through prescriptions/dispensings for the list of medications of interest recorded in the database within 12 months before or on the index date and classified into one of the following drug classes:
 - Bronchodilators: inhaled short-acting muscarinic antagonists (SAMAs), inhaled LAMAs, inhaled short-acting beta2-agonists (SABAs), inhaled LABAs, and fixed combinations of SABAs and SAMAs
 - Inhaled glucocorticosteroids: ICS alone, fixed combinations of SABAs and ICSs, and fixed combinations of LABAs and ICSs
 - Systemic glucocorticosteroids
 - Systemic beta2-agonists
 - Xanthines
 - Roflumilast
- Hospitalisation for COPD exacerbation: an inpatient (primary or secondary discharge) code for COPD (ICD-10 codes: J41-J44), acute bronchitis (ICD-10 codes: J20, J21, J22, J40), or pneumonia (ICD-10 codes J09, J18) within 12 months before or on the index date.

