Annex Table 1-6 (cont'd) Anatomical Therapeutic Chemical codes for comedications

Medication description	ATC code
Drugs for musculoskeletal system	M01A, N02BA, M01B, M01C
Antidepressants	N06A
Antineoplastic agents	L01
Immunosuppressants	L04
Antivirals for systemic use	J05
Hormone-replacement therapy: Estrogens, progestogens, and estrogens in combination	G03C, G03D, G03F
Drugs used in nicotine dependence	N07BA

ATC = Anatomical Therapeutic Chemical; ICS = Inhaled Glucocorticosteroid; LABA = Long-Acting Beta2-Agonist; LAMA = Long-Acting Muscarinic Antagonist; SABA = Short-Acting Beta2-Agonist; SAMA = Short-Acting Muscarinic Antagonist.

1 The national drug code of each database country will be used to identify medications without an individual ATC code.

Source: WHO Collaborating Centre for Drug Statistics Methodology. ATC/DDD Index 2013. Updated 20 December 2012. Available at: [website: whooc.no/atc_ddd_index/](http://website.whooc.no/atc_ddd_index/). Accessed 21 January 2013.

Proprietary confidential information © 2017 Boehringer Ingelheim International GmbH or one or more of its affiliated companies

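### For COPD severity the SAP merges all inhaled bronchodilators into one class without a stated reason, so some patients move from Mild to Moderate; fixed LABA/LAMA products have no class at all

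*SAP*

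**What the plan says.** SAP 5.3.3, Table 8, defines Moderate as "Regular bronchodilator treatment, defined as having at least two prescriptions/dispensings of the same COPD drug class with an interval of ≤ 6 months", within the 12 months before the index date. Mild is the complement: no more than one dispensing of a class, or dispensings more than 6 months apart. The four grades are mutually exclusive and the more severe one prevails.

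The operational definitions then say that drugs in Annex Table 1-6 are "classified into one of the following drug classes". Six bullets follow. The first is "Bronchodilators: inhaled short-acting muscarinic antagonists (SAMAs), inhaled LAMAs, inhaled short-acting beta2-agonists (SABAs), inhaled LABAs, and fixed combinations of SABAs and SAMAs". The second is "Inhaled glucocorticosteroids: ICS alone, fixed combinations of SABAs and ICSs, and fixed combinations of LABAs and ICSs". The other four are systemic glucocorticosteroids, systemic beta2-agonists, xanthines and roflumilast.

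Protocol 9.3.3.4 introduces its list with "Same-class bronchodilators. The following bronchodilators classes will be considered" and gives twelve separate bullets, including one each for SAMA, LAMA, SABA, LABA and SABA/SAMA. Protocol Annex Table 3:1 summarises the Dutch primary care study from which the algorithm was adapted as "At least 2 prescriptions of bronchodilators of the same drug class with a maximum interval of 6 months in 1 year".

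Neither class list, and neither document's ATC annex, has an entry for fixed LABA/LAMA combinations. The source note to SAP Annex Table 1-6 cites "ATC/DDD Index 2013. Updated 20 December 2012".

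**The concern.** The same-class condition is what makes the Moderate grade a measure of repeated use of one type of treatment. Once every inhaled bronchodilator is in one class, the condition no longer distinguishes among them: a single reliever and a single maintenance inhaler count as a repeat. The fixed LABA/LAMA gap works the other way, because a patient can be dispensed such a product every month and still register no class.

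Baseline characteristics of new olodaterol users are a primary objective (protocol Section 8, SAP Section 3), and severity has its own planned results (SAP 7.1.3). The indacaterol figures are meant to put the olodaterol results into perspective. The Mild/Moderate split should therefore follow a rule that the reader can recognise and that has a stated reason.

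**Working it through.** The plan gives no figure to reproduce, so the check compares the two class lists and applies the Table 8 rule under each.

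**Step 1. Class lists.**

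| Drug group | Protocol 9.3.3.4 | SAP 5.3.3 |
|---|---|---|
| SAMA, LAMA, SABA, LABA, SABA/SAMA | five classes | one class |
| ICS, SABA/ICS, LABA/ICS | three classes | one class |
| Systemic steroids, systemic beta2-agonists, xanthines, roflumilast | four classes | four classes |
| Fixed LABA/LAMA | none | none |
| Total | 12 | 6 |

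The first SAP bullet could be read as a heading over five classes. However, the lead-in assigns each drug to one of the classes listed, and the last four bullets are plainly single classes, so the literal reading is one class.

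**Step 2. Apply the Moderate rule** (two same-class dispensings, 6 months taken as 183 days, no Severe or Very severe criterion).

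| Dispensings in the 12 months | Protocol | SAP |
|---|---|---|
| SABA and LAMA, 90 days apart | Mild | Moderate |
| SABA and LABA, 90 days apart | Mild | Moderate |
| ICS and LABA/ICS, 90 days apart | Mild | Moderate |
| SABA and ICS, 90 days apart | Mild | Mild |
| SABA and LABA/ICS, 90 days apart | Mild | Mild |
| SABA and LAMA, 200 days apart | Mild | Mild |
| Two SABA, 90 days apart | Moderate | Moderate |
| Twelve LABA/LAMA, nothing else | Mild | Mild |

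**Step 3. Count the pairs that change.** Twelve protocol classes give 12 × 11 / 2 = 66 pairs of different classes. The merge makes 5 × 4 / 2 = 10 bronchodilator pairs and 3 × 2 / 2 = 3 ICS pairs same-class, so 13 of 66 move from Mild to Moderate. None can move back, because merging only adds same-class pairs. For a reliever (SABA, SAMA, SABA/SAMA) with a maintenance inhaler (LAMA, LABA, ICS, LABA/ICS, LABA/LAMA), 3 × 2 = 6 of 3 × 5 = 15 pairs are same-class under the SAP: those with LAMA or LABA alone.

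**Step 4. One hypothetical patient.** With exactly one SABA and one LAMA dispensing at independent uniform dates in 12 months, P(gap ≤ 6 months) = 1 − (1 − 0.5)² = 0.75. If both are dispensed on one day it is 1.

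**Step 5. Illustration with assumed rates.** Suppose SABA and LAMA dispensings are independent Poisson counts with annual means a and b. For one class with mean m, the patient stays Mild with 0 or 1 dispensing, or with 2 more than 6 months apart (probability 0.25); with 3 or more it is impossible. So M(m) = exp(−m) × (1 + m + m²/8). The Mild share is M(a) × M(b) under the protocol and M(a + b) under the SAP.

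- a = b = 0.5: 0.929² = 86.3% against M(1) = 78.2%, a fall of 8.1 points.
- a = b = 1: 0.782² = 61.1% against M(2) = 47.4%, a fall of 13.7 points.
- a = b = 2: 0.474² = 22.4% against M(4) = 12.8%, a fall of 9.6 points.

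These rates are assumptions, not figures from the documents.

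**Step 6. Is there a stated reason?** SAP Section 4, item 3, says the severity definition was modified to resemble GOLD 2016. In Table 8 the GOLD footnote is attached only to the exacerbation criterion in the Severe row. The Moderate row carries footnotes 1 and 2, which say that two published definitions also include the criterion. Protocol Annex Table 3:1 summarises the one in footnote 2, a UK general practice database study, as two prescriptions of the same COPD drug. None of this explains the merge.

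**The case against.** The strongest reply is that Table 8 labels Moderate as regular bronchodilator treatment. Two bronchodilator dispensings of any kind within 6 months is an arguable proxy for that, and nothing in the documents shows that such a patient is truly Mild. This stands as far as it goes: a merged class could be defended, but the SAP does not defend it. SAP 7.1.3 also reports the criteria met within each grade, and the comedication tables show part of the treatment mix. Section 9.2, which holds the database-specific definitions and is not in the text available, may refine the classes.

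Several stronger readings are tempting but not supported.

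- A reader might infer that any reliever plus any maintenance inhaler now counts as Moderate. It does not: ICS and LABA/ICS sit in a different SAP class.
- A reader might infer that the results can no longer be compared with published work. The documents do not list the source study's classes. The protocol also calls its own version modified and adds criteria such as pneumonia and emphysema.
- A reader might infer that the change was wholly undeclared, or that the SAP created the LABA/LAMA gap. A modified severity definition is declared, and the gap is already in the protocol.
- A reader might infer from the 2012 source note that the code list was never revised. The SAP annex adds seven LABA/ICS codes that the protocol lacks.
- A reader might want two different dispensing dates to be required. Neither document sets a minimum interval, and the summaries of the cited definitions in Protocol Annex Table 3:1 contain no such rule, so the merge did not create that feature.

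**Conclusion.** The point holds in a limited form. The SAP departs from the protocol's drug classes without a stated reason. The departure regrades as Moderate a patient who meets three conditions: one short-acting bronchodilator plus one single-agent LAMA or LABA (or another of the 13 newly same-class pairs), a gap of 6 months or less, and no Severe or Very severe criterion. Patients who already have two dispensings within one protocol class no more than 6 months apart do not change grade.

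Separately, a patient treated only with a fixed LABA/LAMA product would be graded Mild however often it was dispensed, absent a Severe or Very severe criterion. That such products were in use in the study years is an assumption.

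The share of patients affected cannot be obtained from the documents. The 75% describes one hypothetical patient, and the falls of about 8 to 14 points rest on assumed dispensing rates. The consequence is confined to a descriptive baseline characteristic, reported mainly for COPD patients aged 40 years or older in the Netherlands and Denmark. SAP 5.3.3 does not describe severity in the French database, and off-label prevalence does not use the severity grade.

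**What to change.** In SAP 5.3.3, reconcile the class list with protocol 9.3.3.4 by counting same-class dispensings within the protocol's separate classes. If the sponsor prefers the merged classes, state the reason in SAP Section 4 and show the severity distribution under both groupings.

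Add a class for fixed LABA/LAMA combinations. Update the respiratory part of Annex Table 1-6 to the ATC edition in force at data extraction, including the LABA/LAMA codes. While doing so, check the placing of each drug: the annex lists indacaterol among the SABAs, although the protocol describes it as a LABA, and this matters once the classes are separate. Check the database-specific specifications in Section 9.2 for consistency with the revised list.

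The cost is SAP wording and a regrouped code list, with no new data. The downside is that more patients will be graded Mild than under the merged class.

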General practitioner outpatient diagnoses	Yes, in data subset PHARMO-GP ¹	No	Yes (a panel of 1,200 general practitioners) ²
Specialist diagnoses	Yes, those in the hospital (no outpatient hospital or non-hospital clinics) or as communicated to and recorded by the GP in PHARMO-GP (primary care)	Yes, those in the hospital (inpatient diagnosis) and hospital outpatient clinics (outpatient diagnosis) (not outside the hospital)	Yes (a panel of 40 pulmonologists) ³
Pharmacy-dispensed medications	Yes	Yes	No
Prescribed medications	Yes, in data subset PHARMO-GP ¹	No	Yes

GP = General Practitioner; IMS = IMS Health Information Solutions; PHARMO = PHARMO Database Network; RWE LPD = Real-World Evidence Longitudinal Patient Database.

- 1 For this study, data from the Out-patient Pharmacy Database and the Hospitalisation Database are available for the overall source population (approximately 4 million patients covered); the subcohort PHARMO-GP includes approximately 1 million patients with data in the Out-patient Pharmacy Database, the Hospitalisation Database, and the General Practitioner (GP) Database. The Out-patient Pharmacy Database will be used to identify medication use.
- 2 The GP panel covers a population of approximately 1.8 million active patients.
- 3 The pulmonologist panel covers a population of approximately 55,000 active patients.

The coding of diagnoses, procedures, and medications varies across databases ([Table 3](#)).

Proprietary confidential information © 2017 Boehringer Ingelheim International GmbH or one or more of its affiliated companies

Table 3 Types of diagnosis, procedures, and medication codes in the study databases

Type of code	PHARMO, The Netherlands	National Registers, Denmark	IMS RWE LPD, France
Diagnoses	Hospital: ICD-10 ¹ Primary health care: ICPC ²	ICD-10	Local in-house thesaurus that can be mapped to ICD-10
Procedures	CBV	NCSP version 1.16, 2012	Local in-house thesaurus that can be mapped to ICD-10
Medications	ATC	ATC	/ EphMRA mapped to ATC

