6.5 HANDLING OF MISSING DATA AND OUTLIERS

The extent of missing data will be evaluated and described. Due to the nature of this study, no imputation of missing data is planned. Missing values are expected in some sociodemographic variables depending on the definition used and in variables related to exposure characterisations such as strength or daily dose. Degree of missingness will depend on the database, and some data sources will have variables that are not available, such as oxygen therapy in PHARMO and hospitalisations in IMS RWE LPD. Diagnoses, prescriptions, and dispensings can be identified in the databases only if they are recorded. Thus, all patients with a certain diagnosis/dispensing in the database will be coded as having

Proprietary confidential information © 2017 Boehringer Ingelheim International GmbH or one or more of its affiliated companies

the respective condition/exposure to the respective drug. All others will be coded as not having the disease/not being exposed to the drug. Therefore, uncoded diagnoses/dispensings may result in misclassification and not in missing values.

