Annex Table 1-7 Database-specific codes for nebulisers in PHARMO

Devices	code
RESPIFLO VERNEVEL ADAPTER	14057816
VERNEVELAAR	14684217
MEDICIJN VERNEVELSET KENDALL MET AER MASKER KIND	14824256
MEDICIJN VERNEVELSET KENDALL MET AER MASKER VOLWAS	14824264
MONDSTUK VERNEVELAAR KENDALL LOS	14825678
MEDICIJN VERNEVELAAR KENDALL LOS	14825686
MEDICIJN VERNEVELSET KENDALL MET MONDSTUK	14825694
RESPIFLO CUP VOOR UN VERNEVELAAR 145ML	14826836
HUDSON ISONEB VERNEVELAAR	15136620
OMRON COMP AIR COMPRESSORVERNEVELAAR	15214508
OMRON COMP AIR ELITE COMPRESSORVERNEVELAAR	15214532
OMRON COMP AIR PRO COMPRESSORVERNEVELAAR	15214540
PARI EFLOW OPBERGZAK TBV VERNEVELAAR	15502155
PARI EFLOW VERBINDINGSKABEL NAAR VERNEVELAAR	15502198
PARI EFLOW VERNEVELSET INCLUSIEF MESH	15502201
PARI SINUS VERNEVELAAR COMPLEET	15502309
PARI TURBOBOY N MEDICATIE VERNEVELAAR COMPLEET	15502333
PARI LC PLUS VERNEVELAAR	15559025
PARI LC SPRINT VERNEVELAAR	15559033
OMRON COMP AIR COMPRESSORVERN COMPACT GEEL KIND	15910253
OMRON COMP AIR COMPRESSORVERNEVELAAR COMPACT WIT	15910261
VERNEVELSET INTERSURGICAL INCL FILTER Z FLOWMETER	16135067
CIRRUS 2 VERNEVELAAR	16135091
CIRRUS 2 VERNEVELAAR + KINDERMASKER + SLANG	16135105
CIRRUS 2 VERNEVELAAR + MONDSTUK + SLANG	16135113
VERNEVELMASKER INTERSURGICAL ECO KIND	16135121
T-STUK INTERSURGICAL MET VEER VOOR VERNEVELING	16135199

Proprietary confidential information © 2017 Boehringer Ingelheim International GmbH or one or more of its affiliated companies

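### Unless Section 9.2 handles it, PHARMO COPD severity is distorted by data capture: outside the GP subset a recent inpatient code both admits a patient and makes that patient Severe, and oxygen cannot be seen

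*SAP*

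**What the plan says.** **Entry.** SAP 5.3.3 describes severity in new users aged 40 or older who "have a recorded diagnosis of COPD (with or without a diagnosis of asthma) ever before or up 30 days after the index date". In ICD-10, COPD is J41-J44 (SAP Table 5). The PHARMO look-back runs to 1998, or to 2006 for the GP subset (SAP 5).

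**Diagnosis sources.** In SAP Table 2, PHARMO has GP diagnoses only in PHARMO-GP and no hospital outpatient diagnoses. Its specialist diagnoses are "Yes, those in the hospital (no outpatient hospital or non-hospital clinics") or those passed on to a GP in PHARMO-GP. Footnote 1 gives about 4 million patients overall, and "the subcohort PHARMO-GP includes approximately 1 million patients".

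**Severe.** The hospitalisation criterion is "an inpatient (primary or secondary discharge) code for COPD (ICD-10 codes: J41-J44"), or for acute bronchitis or pneumonia, in the year up to and including index. A second route is two or more exacerbations treated outside hospital. These can be counted from antibiotic and systemic steroid dispensings.

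**Very severe.** The inputs are oxygen, nebuliser therapy, or emphysema (J43) at any time up to index. A patient who meets several categories takes the highest.

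**Unavailable data.** SAP 6.5 states that "some data sources will have variables that are not available, such as oxygen therapy in PHARMO and hospitalisations in IMS RWE LPD". Of patients without a record it says: "All others will be coded as not having the disease/not being exposed to the drug". For France, 5.3.3 draws a consequence: "Because data on hospitalisations are not available in the IMS RWE LPD database, COPD severity will not be described in this database". The public text has no matching rule for PHARMO.

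**Nebulisers.** Annex Table 1-7 lists PHARMO devices and accessories, including a storage bag ("PARI EFLOW OPBERGZAK TBV VERNEVELAAR"). Annex Table 1-8 lists Danish nebulised drugs.

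**The concern.** Describing the baseline characteristics of olodaterol users is a primary objective, and COPD severity is one of those characteristics. In most of PHARMO's coverage, the record that shows a patient has COPD is of the same kind as the record that classes the patient as Severe. Patients managed only in primary care are not in the table at all, so the non-GP patients who do appear are selected on admission. SAP 7.3 recognises that many COPD patients may never have been hospitalised, but applies this only to the off-label estimate.

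Two groups with different capture would then be pooled into one PHARMO distribution. The top category would also lack one input that it keeps elsewhere. A reader who sets PHARMO beside Denmark could take a difference in capture for a difference in patients.

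The off-label classification is a separate matter and is not at issue here.

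**Working it through.** The documents give no expected severity distribution, so there is no planned figure to reproduce. The first and last steps compare definitions. The steps between are illustrations on assumed inputs.

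**1. Overlap of entry and category, PHARMO outside the GP subset**

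| Only qualifying inpatient code | Admits? | Category it forces |
|---|---|---|
| J41, J42 or J44 in the year up to and including index | Yes | At least Severe |
| J43 at any time up to index | Yes | Very severe |
| J41, J42 or J44 more than a year before index | Yes | None; Mild or Moderate possible |
| J41, J42 or J44 on days 1-30 after index | Yes | None; Mild or Moderate possible |

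Secondary discharge codes count. An admission for another cause with COPD listed second therefore meets Severe, although SAP Table 7 counts COPD hospitalisations by primary diagnosis only.

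**2. Coverage.** (4 - 1)/4 = 75% of PHARMO patients are outside the GP subset. This is a share of coverage, not of the severity table.

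**3. Size of the shift (all inputs assumed).** Let
- e = share of COPD users with any qualifying inpatient code;
- f = share of those whose code falls in the year up to and including index;
- x = share Severe or worse by another route, taken as equal in both groups.

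Full capture: S_full = ef + (1 - ef)x. Inpatient-only capture: S_inp = f + (1 - f)x.

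With e = 0.3, f = 0.5, x = 0.2:
- S_full = 0.15 + 0.85 × 0.2 = 0.32
- S_inp = 0.50 + 0.50 × 0.2 = 0.60

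If PHARMO-GP sees all COPD users and use is equal in both parts, the non-GP share of the table is w = 3e/(3e + 1). The pooled figure is then w·S_inp + (1 - w)·S_full. With f = 0.5 and x = 0.2:

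| e | S_full | S_inp | Ratio | w | Pooled |
|---|---|---|---|---|---|
| 0.2 | 28% | 60% | 2.14 | 38% | 40% |
| 0.3 | 32% | 60% | 1.88 | 47% | 45% |
| 0.5 | 40% | 60% | 1.50 | 60% | 52% |
| 0.8 | 52% | 60% | 1.15 | 71% | 58% |

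Over f = 0.25 to 1.0 and e = 0.2 to 0.8, the ratio runs from 1.1 to 2.8 when x = 0.2. When x = 0 it equals 1/e, from 1.25 to 5.0.

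**4. Oxygen (assumed).** Let o be the share on oxygen and v the share with a nebuliser or emphysema record, taken as independent. Very severe is 1 - (1 - o)(1 - v) with oxygen data and v without, so the loss is o(1 - v). For o = 2-10% and v = 5-40%:
- smallest loss: 0.02 × 0.60 = 1.2 percentage points, 3% of a category of 41.2%;
- largest loss: 0.10 × 0.95 = 9.5 points, 66% of a category of 14.5%.

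**5. Direction for Very severe.** Missing oxygen lowers it. Selection through inpatient J43 raises it in the non-GP group. The nebuliser input differs in kind between PHARMO and Denmark. The net effect cannot be signed.

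**The case against.** **Section 9.2.** The strongest objection is that 5.3.3 says its definitions will be adapted to each source and points to Section 9.2, which is not in the public text. That section may already restrict PHARMO severity to the GP subset or say how oxygen is treated. This stands, and makes the point conditional.

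**Planned disclosure.** SAP 7.1.3 will describe the criteria used in each source and report counts by criterion within each category. The analyses are descriptive and run by database, and no PHARMO-Denmark severity contrast is planned. This limits the harm. It does not separate hospital-selected patients from GP-identified ones, so it does not replace a split by GP linkage.

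**Stronger readings the documents do not support:**
- *That entry and Severe are the same test, so capture sets the categories.* The entry window is far wider than the Severe window. Mild, Moderate and the dispensing route to Severe use pharmacy data held for all of PHARMO.
- *That oxygen is definitely coded as absent.* SAP 6.5 suggests it, but 5.3 limits the absence rule to covariates available in the data. The handling is unsettled.
- *That Very severe is understated throughout PHARMO.* The J43 overlap pushes the other way.
- *That three quarters of the severity table is affected.* On the assumptions above the share is 38-71%.
- *That PHARMO should lose its four-level split, or accessories their place in the nebuliser list.* Two of three Very severe inputs remain, and an accessory may still mark a nebuliser user. These are preferences. Denmark has no GP diagnoses under the SAP either, though its hospital clinic codes can admit a patient without an admission.

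**Conclusion.** The point holds, provided Section 9.2 does not already resolve it. Outside PHARMO-GP, inpatient codes alone identify COPD. Those in the year up to and including index also meet Severe, and inpatient J43 at any time up to index also meets Very severe. Severe-or-worse is therefore likely to be inflated in non-GP patients relative to PHARMO-GP.

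The documents do not allow the size to be estimated. The 60% against 32%, and the pooled 45%, rest on assumed values of e, f and x, on equal x in both groups and, for the pooled figure, on complete GP capture and equal use. The excess shrinks as inpatient capture approaches completeness.

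Very severe in PHARMO lacks one of its three inputs, and its net direction is unknown. This is a real but limited distortion of a descriptor under a primary objective.

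**What to change.** Unless Section 9.2 already provides for it:

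1. In Shell Table 9, report PHARMO severity separately for PHARMO-GP and non-GP patients, with PHARMO-GP as the main presentation.
2. State in SAP 5.3.3 and 6.5 that oxygen in PHARMO is not assessable, and show it that way in the table instead of as absent.
3. If PHARMO and Denmark are compared, add a combined row for Severe or very severe and keep the four levels.
4. Footnote that PHARMO nebuliser codes identify devices and Danish codes identify nebulised drugs.

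This takes SAP wording and a table shell, with no new data; SAP Table 6 already uses PHARMO-GP for smoking status. The cost is smaller cells in the PHARMO table.
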